### **3. Protection from risk.**

This procedure is introduced voluntarily and participants or other legal representatives of the patient have the right to refuse the examination. In order to exclude exacerbations of pre-existing chronic diseases, a thorough medical history will be taken and concomitant pathology taken into account.

**4.** The potential benefit for the participant is the possibility of early nutritional support in cancer-surgical patients, receiving timely recommendations on lifestyle management, prevention, treatment and rehabilitation.

### **5. Alternatives for the participant.**

Participants have the right to refuse the proposed research method. In this case, treatment will be carried out using the traditional method. Without the written consent of the participant or legal representatives, the patient cannot be included in the study.

## **V. Identification of Study Participants, Recruitment and Consent**

Before each study, patients are explained the goals and objectives of the study, informed of their right to refuse examination at any stage, and written consent to undergo treatment is obtained.

### **1. Methods for identifying participants and recruiting them.**

The subjects will be selected by a continuous method during screening and patients with cancer pathology will be randomly selected.

### **2. Consent process.**

The consent process will be carried out by the researcher in the form of written consent after explaining to the participants the purposes and methods of the study, as well as all potential risks, in accordance with the norms of the standard of Good Clinical Practice (GCP).

### **3. Participant's condition.**

It is necessary to obtain informed consent from the patient in person. If it is not possible to obtain informed consent, the patient is not included in the study.

### **4. Understanding.**

After the goals and objectives of the study have been explained and potential benefits and risks have been discussed with the participant, the participant will be asked to sign an informed

consent form. The patient may refuse to participate in the study if he wishes. Children and incapacitated adults will not be included in the study.

**5. Consent forms.**

The informed consent form is presented in Appendix 1 to this protocol.

**6. Documentation of consent.**

Informed consent, in two copies, is voluntarily signed by the study participant and the research physician, and one copy remains with the research subject, the second is stored in the study file and the registration journal of the research topic.

**7. Participation price.**

There is no cost of participation for patients.

**8. Participation fee.**

There is no payment to the participant.

## Report

№ MUK\_NutS-HPD-PO\_2017 from March 17, 2020

Karaganda Medical University

This study was approved by the Karaganda Medical University of the city of Karaganda of the Republic of Kazakhstan. Research and Ethics Committee of February 12, 2020 Protocol №4. All methods were carried out in accordance with ethical principles and rules approved by the ethics committee.

The clinical trial period was started in January 2017 and completed in March 2020

**Purpose of the study:** To improve the nutritional status of cancer patients after operations performed in the hepatopancreatoduodenal zone in connection with malignant neoplasms, through a comprehensive comparative analysis of the effectiveness of isolated enteral, isolated parenteral and mixed type of nutritional support in the early postoperative period.

### Scientific hypothesis

Complete and comprehensive nutritional support for patients operated on for malignant neoplasms of the hepatopancreatoduodenal zone, in the form of various approaches and methods of delivering nutrients to patients in the early postoperative period, allows to improve the functional activity of the gastrointestinal tract of patients, stabilize the level of carbohydrate, protein, basal metabolism, accelerate transfer to full enteral nutrition and reduce the length of stay in the intensive care unit and, ultimately, in the hospital.

### Research objectives:

1. To conduct a comparative assessment of the dynamics of nutritional deficiency and nutritional status of patients operated on for malignant tumors of the hepatopancreatoduodenal zone in the early postoperative period during isolated enteral, isolated parenteral and mixed types of nutritional support.
2. To analyze the dynamics of the state of protein and carbohydrate metabolism, the consistency of liver function in cancer patients operated on for malignant tumors of the hepatopancreatoduodenal zone, against the background of isolated enteral, isolated parenteral and mixed type of nutritional support in the early postoperative period.
3. To determine the degree of effectiveness of these methods of nutritional support in this category of patients based on the totality of the results of assessing nutritional status and the dynamics of the level of basal metabolism in these patients in the early postoperative period.

Researched 91 patients, will be divided into 3 groups:

1. The first group (n=31) included patients who received enteral nutrition (EN) after surgery.
2. The second group (n=30) included patients receiving parenteral nutrition (PN).
3. The third group (n=30) receiving mixed nutrition (MN), as is commonly considered the method of partial parenteral nutrition, in the early postoperative period.

### Clinical research program:

The study was carried out on the basis of the KGP at the RVC "Multidisciplinary Hospital No. 3 of the city of Karaganda". Venue: intensive care unit.

To identify nutritional deficiency, there are screening methods recommended by the international clinical nutrition associations ASPEN (American Society for Parenteral and Enteral Nutrition - ASPEN) and ESPEN (European Society for Parenteral and Enteral Nutrition - ESPEN), including questioning patients, using standard anthropometric and laboratory data, which makes it possible to assess nutritional status and the degree of its impairment.

At the first stage, the clinical condition of the patient was assessed using the Nutritional Risk Screening (NRS, 2002), Subjective Global Assessment (SGA) and Nutritional Risk Index (NRI) protocols before surgery and on the 5th, 10th, 15th day after surgery .

A comparative assessment of the clinical effectiveness of the use of types of nutritional nutrition in a complex of therapeutic measures after these operations in the hepatopancreatoduodenal zone was carried out.

Some nutritional status indicators available for determination at the Oncology Clinic were assessed - body mass index (weight measurements were carried out before surgery, on the **5th, 10th and 15th** days), basal metabolic rate (calculated using the Harris-Benedict equation, based on anthropometric data of the patient (gender, age, weight and height).), laboratory parameters: blood hemoglobin, lymphocytes, total protein, serum albumin, serum transferrin, total bilirubin and direct, ALT, AST, which are related to the traditional method for assessing nutritional status.

Additionally, we assessed the duration of postoperative gastrostasis, the timing of the onset of intestinal motility, the appearance of stool, the return to a normal diet, the duration of patients' stay in the ICU, the repeated admission of patients to the ICU and the duration of the postoperative bed-day, and the incidence of complications was calculated.

## **Methods of statistical data analysis**

All patients hospitalized for special treatment with a verified diagnosis of a malignant neoplasm were subjected to the study in the abdominal department of the KGP at the Regional Oncological Dispensary, Karaganda.

The quantitative and qualitative indicators obtained during the study were analyzed using descriptive and analytical statistics methods. For statistical processing of qualitative (diagnosis codes, dichotomous data) and quantitative variables: symptom intensity, severity, frequency of occurrence, we used the calculation of the median level (Me) with 25%-75% quartiles (Q25; Q75) and the calculation of the arithmetic mean (M) with error (m) and 95% confidence interval (95% CI), standard deviation (s). Quantitative variables were checked for normality of distribution using the Kolmogorov-Smirnov test, as well as the module of Skewness and Kurtosis for quantitative variables  $| \leq 2 |$ . Differences in the 3 groups of patients for quantitative variables corresponding to a normal distribution were identified using the Student's t test for unrelated groups, first for 3 or more groups, and then in pairs for each pair using the Student's t test. Differences for rank variables, or quantitative but not normally distributed for unrelated groups, were determined by the Kruskal-Wallis test or median test for 3 groups, and then pairwise or non-parametric Mann-Whitney test for each of the 3 pairs (groups 1 and 2, groups 1 and 3, groups 2 and 3), and for related groups (dynamic observations) by the Kendall test for 3 groups and then by the Wilcoxon test (Wilcoxon) for each of the 3 pairs (baseline, after 5 days and after 10 days).

Correlation was performed for quantitative variables according to Pearson and for rank variables according to Spearman. Statistical processing of the results was carried out using the Statistica program version 10.

**Results and discussion.** The nutritional status of patients in all three groups before surgery and during the 10-12 days of the postoperative period according to the methods of assessing nutritional status NRS, SGA and NRI was assessed as normal, moderate and severe malnutrition

As can be seen from the presented data, in the preoperative period, according to the SGA assessment, 24 patients in the enteral group, 19 patients in the parenteral group, and 17 patients in the mixed group had normal nutritional status before surgery, with variations relative to patients with moderate to severe malnutrition. Assessment of nutritional status before surgery using the NRI scale allowed us to confirm the nutritional status of the vast majority of patients in all groups as relatively normal

Thus, in 62 of the 91 patients examined, the NRI was assessed as true negative (normal nutritional status), in 26 as true positive (moderate malnutrition), and in 3 as severe malnutrition. Data from the NRI method during this time period had a strong correlation with the results of the SGA scale ( $p < 0.005$ ).

On the 10-12th day of the postoperative period in patients of the “enteral” group, the results of the assessment on the SGA scale remained unchanged; according to the NRI rating scale, there was an increase in “moderate malnutrition” per patient (25%).

With parenteral nutritional support, 17 patients had “normal nutrition”, 14 patients had moderate malnutrition, with regression of “severe malnutrition” in 1 patient. In the mixed nutrition group, there was a complete elimination of signs of “severe malnutrition” by 100% according to the given scales ( $p < 0.005$ ).

In patients of all study groups, throughout the entire period of nutritional support, fluctuations in the level of basal metabolism were observed in average values of  $335.89 \pm 53.6$  kcal/day (13.44%) from the initial value - 1-2 days of the postoperative period and were due to variability body mass index and the dynamics of the temperature curve after surgery.

In patients in the groups with enteral and parenteral nutrition, by the end of these types of energy subsidies (days 10-15), the level of basal metabolism was observed to approach its initial values -  $2500.1 \pm 353.4$  kcal/day and  $2350.0 \pm 330.5$  kcal/day days accordingly. With a mixed type of nutrition, there was a statistically significant decrease in the level of basal metabolism by 6.78% ( $2250.0 \pm 105.2$  kcal/s), which allows us to conclude that patients' energy costs are more effectively covered with this option of nutritional support in a comparative aspect with isolated types nutrition ( $p < 0.03$ ).

This fact was obviously associated with the preservation/restoration of parietal digestion in the gastrointestinal tract in the early postoperative period, despite postoperative intestinal paresis of varying degrees, and the involvement of nutrients in anabolic processes with parallel “covering” of the required daily caloric intake by parenteral administration of mixtures.

Evaluation and subsequent analysis of the results of laboratory examination in groups of patients in a comparative aspect showed a relatively slow and gradual decrease in the level of total blood protein by the 5th day of the postoperative period, on average, by  $6.8 \pm 0.95\%$  of the initial values, which,

apparently, was due to increased catabolism and ongoing protein losses (exudation, drainage, etc.) with a fairly significant increase by the end of nutritional support.

Thus, a statistically significant increase in the level of total blood protein was noted in the mixed nutrition group ( $p = 0.004$ ). In the groups with enteral and parenteral nutrition, differences in the dynamics of total protein levels were found at the level of a statistical trend:  $p=0.108$  and  $p=0.129$ , respectively.

When analyzing changes in the number of blood lymphocytes, it should be noted that before the operation the relative value of lymphocytes in the groups was significantly reduced ( $25.9\pm3.7\%$ ), but taking into account the methods and volumes of the operation, the tension of the cellular and humoral parts of the immune system, the dynamics of their level was expressed in the form of a statistically significant increase in the level of lymphocytes in the postoperative period by 10-12 days.

Thus, there was a steady increase in the level of blood lymphocytes by the 10th day of the postoperative period in all groups, on average by 8.95% ( $p = 0.000$ ), by 10.35% ( $p = 0.003$ ), by 10.91% ( $p = 0.000$ ) respectively.

This dynamics reflects the positive effect on the immune status of patients of the combined use of parenteral and enteral types of nutritional support in the postoperative period in this group of patients.

A comparative analysis of the dynamics of ALT and ASAT values in all patients in the study groups on the 2-3, 6-8, 10-12 days of the postoperative period reflected an excess of their normal values after surgery in some patients tens of times in the first day of the postoperative period. These changes can be explained, first of all, by the surgical intervention itself and its volume, the underlying disease of the hepatopancreatoduodenal zone and the associated cytolytic syndrome against the background of cholestasis [9,10,11].

In terms of assessing the dynamics of blood transaminase levels, in the majority of patients in the first group (78.2%), by the 5th and 10th days there was a decrease in ALT and AST values, on average, by 32.1 and 40.15%, respectively.

In the overwhelming number of patients in the second group (81.6%,  $n=26$ ), a statistically significant decrease in the level of these blood transaminases was also recorded, on average by 72.2% by the fifth day and 66.7% by the 10th day of the postoperative period from level of their initial indicator.

With a mixed type of nutritional support, by the 5th day of the postoperative period, the average significant decrease in transaminases was, on average, up to 72.6% of the initial values ( $p = 0.000$ ); by the 10th day of the postoperative period, their level decreased to 63.8% from the previous achieved value of 5 days ( $p=0.008$ ).

When comparing analyzes of the level of total blood bilirubin in patients of all nutrition groups, there was a strong direct correlation with a decrease in the level of blood transaminases, which, apparently, was also due to the creation of sufficient intraoperative bile outflow due to drainage of the biliary tract and elimination of the cause of obstructive jaundice (tumor).

However, high values of total blood bilirubin that persisted on the first day after surgery were due to temporary swelling of the biliary tract, which caused the excess of the norm by more than 10 times ( $p = 0.000$ ).

On days 5-7, there was a tendency towards a 5-6 fold decrease in its level from the initial values, which gradually decreased to normal values by days 10-12 and in some patients persisted until discharge from the hospital ( $p = 0.004$ ).

In comparative quantitative terms, in patients of the first group, a decrease in the level of total bilirubin was recorded, on average, by 12.7% only by the 10th day after surgery ( $p = 0.187$ ). In the second group, there was a decrease in the level of total blood bilirubin by the 5th day, on average, by 40.09% and by the 10th day by 45.0% from its initial values (preoperative period), ( $p = 0.002$ ).

In patients of group 3, there was a slower regression of this indicator: a decrease, on average, by 20.0% by the 5th day and by 44.0% by the 10th day of the postoperative period [1,5,12].

[figure not shown]

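### The normality check that chooses between t tests and rank tests names no correction for estimated parameters and no rule for combining its two parts, so at about 30 patients per group it can pass skewed outcomes as normal

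*Combined protocol and SAP*

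**What the plan says.** The check is set out in the report, under Methods of statistical data analysis. The sentence begins "Quantitative variables were checked for normality of distribution using the Kolmogorov-Smirnov test" and continues "as well as the module of Skewness and Kurtosis for quantitative variables", with an absolute limit of 2.

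The result routes each variable:

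- If judged normal: "Differences in the 3 groups of patients for quantitative variables corresponding to a normal distribution were identified using the Student's t test for unrelated groups", then pairwise t tests.
- If judged not normal: "quantitative but not normally distributed for unrelated groups, were determined by the Kruskal-Wallis test or median test for 3 groups", then pairwise Mann-Whitney tests.
- For repeated measurements within a group, the only tests named are Kendall and Wilcoxon. No paired t test is mentioned.

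The same section lists medians with quartiles and means with error, SD and 95% CI. It ties neither to the result of the normality check.

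The groups have 31, 30 and 30 patients (Research objectives). Objective 2 covers liver function. In Results and discussion, the ALT and AST paragraph says the values "reflected an excess of their normal values after surgery in some patients tens of times", and total bilirubin is put at more than ten times the norm.

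The section does not state the significance level of the normality test, which Kolmogorov-Smirnov p-value was read, whether testing was per group or pooled, or how the two checks combine. The earlier protocol section on data analysis names Student's t and Pearson correlation but no normality check.

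**The concern.** The ordinary Kolmogorov-Smirnov critical value is derived for a normal curve whose mean and SD were fixed before the data were seen. No such values are given anywhere in the documents, so both must come from the sample being tested. A curve fitted to the data lies closer to them than a pre-fixed curve would. The ordinary critical value is then too large and the test rejects too seldom. The Lilliefors version corrects this, but it is not named.

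At stake is whether the check does its job. ALT, AST and bilirubin have long right tails by the report's own description, and ICU and hospital stay are commonly skewed too. If the check passes such variables, the group comparison becomes one of arithmetic means by Student's t. The reader also cannot reconstruct which route a variable took, because the combining rule is missing.

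**Working it through.** The documents give no figure for this check, so there is nothing to reproduce beyond 31 + 30 + 30 = 91, which agrees.

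**Inputs from the documents.** About 30 per group; a Kolmogorov-Smirnov test; a limit of 2 on absolute skewness and kurtosis.

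**Assumptions, because the documents are silent.** A 5% level; ordinary p-value; testing within each group; excess kurtosis (raw kurtosis is 3 for a normal curve, so a limit of 2 would reject normal data); second check flags if either measure exceeds 2. Skewed data are log-normal with log-SD 0.5, 0.8 or 1.0, because no spread is given for ALT, AST or bilirubin.

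**Step 1: calibration.** The statistic is D = max over i of { i/n − Φ(z_i), Φ(z_i) − (i−1)/n }, where z_i = (x_(i) − sample mean)/sample SD. At n = 30 the ordinary 5% critical value is 0.242. The simulated critical value that allows for estimating mean and SD is 0.159. With the ordinary value, truly normal samples are rejected in about 0.01% of cases or fewer, against the nominal 5%.

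**Step 2: detection of skew** (simulation, n = 30).

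| | log-SD 0.5 | 0.8 | 1.0 |
|---|---|---|---|
| Plain K-S rejects | 4% | 23% | 43% |
| Lilliefors rejects | 48% | 82% | 93% |
| Shapiro-Wilk rejects | 72% | 97% | 99% |
| Called normal, either check suffices | 62% | 34% | 21% |
| Called normal, both must flag | 97% | 80% | 61% |

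The last two rows show how much depends on the unstated combining rule.

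**Step 3: where the check works better.** At log-SD 1.25 and 1.5, plain K-S alone rejects 67% and 84%. With the second check, if either suffices, 90% and 95% are caught. If all 91 patients are pooled, only about 3% of samples at log-SD 0.8 and 0.2% to 0.3% at 1.0 pass under the same rule, although 34% still pass at 0.5.

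**Step 4: effect on the group comparison.** With 30 against 30, Student's t on such data has type I error of 4.7%, 4.2% and 4.0%. If every sample at log-SD 1.0 went to the t test, power for a 1.8-fold ratio would be 44%, against 59% for Mann-Whitney. That is an upper bound. If both arms must pass before a t test is used and either check can reject, the share sent to t is about 0.62² = 38%, 0.34² = 12% and 0.21² = 4%. The t test is therefore used least where it loses most. Over the whole procedure the loss is about 1 to 5 points against a log-scale analysis, and almost nothing against Mann-Whitney.

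**Step 5: confidence intervals, apart from the check.** In all samples, gated or not, the t-based 95% CI for the arithmetic mean covers about 94%, 91% and 88%.

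**The case against.** The strongest reply is that the skewness and kurtosis limit stands in the same sentence and does much of the work. Values tens of times normal suggest strong skew, which is where the combined check does best. This stands, but only if either check is enough to reject. The plan does not say so, and moderate skew passes often on either reading.

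Three stronger readings are tempting, and the documents do not support them.

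- *The test almost never rejects.* That is true of normal data, where not rejecting is correct, and of mild skew. It is not true at log-SD 1.0 and above.
- *The liver outcomes were analysed by t tests.* A reader might infer this from the average percentage falls with p-values in Results and discussion. The test behind those p-values is not named. Most describe change within a group, for which the methods name only rank tests.
- *The check produces confidence intervals that are too narrow.* In samples that pass the plan's check (either suffices), coverage is about 92%, 84% and 75%, which looks like damage done by the check. It is a selection effect: samples that pass tend to be those that missed the tail. Samples passing Lilliefors do slightly worse, at about 91%, 80% and 63%. Means with CIs are also listed regardless of the check.

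Use of the ordinary p-value is itself inferred from the absence of any named correction.

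**Conclusion.** The point holds as a defect in how the analysis is chosen. The plan selects tests with a check that is under-specified. On the plain, per-group reading, its Kolmogorov-Smirnov part has a size near 0% and detects 4% to 43% of the skewed samples considered, where a calibrated version detects 48% to 93%. The second screen makes up part of this: 21% to 62% of samples still pass if either check can reject, and 61% to 97% if both must.

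Skewed group comparisons of ALT, AST, bilirubin, ICU stay and hospital stay can therefore reach Student's t. Whether any did is not documented. The consequence for the tests is modest: no type I inflation of note and about 1 to 5 points of power. No reported p-value is shown to be wrong on this ground. The under-coverage of mean-based intervals is a separate matter that would remain with a better normality test.

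The sizes rest on the assumed log-SDs, the 5% level and per-group testing. Strong skew (if either check can reject) or pooling at 91 would shrink the problem considerably.

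**What to change.** In Methods of statistical data analysis, remove the normality pre-test for ALT, AST, bilirubin and the duration outcomes. State one fixed analysis for the group comparison: either the log scale, with geometric means and ratios and their 95% CIs, or medians with Kruskal-Wallis followed by Mann-Whitney. The log-scale option also replaces the mean-based intervals that under-cover.

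If a normality check is kept for other variables, use Shapiro-Wilk or the Lilliefors-corrected Kolmogorov-Smirnov test. State its level, whether it is run per group, and how it combines with the skewness and kurtosis limit. Then re-run any variable that was placed in the t-test branch, and name the test beside each reported p-value.

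The cost is a short change to the methods text and a re-run on existing data. Some results will be reported as medians or geometric means instead of arithmetic means.

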## **2. Data analysis and monitoring.**

Statistical processing of the obtained data will be carried out using the application package STATISTICA version 7.0, taking into account computational methods recommended for biology and medicine. Statistical research methods include: calculation of median and mode, standard deviation. To determine the reliability of the obtained indicators, Student's t-test will be used. Also calculate the pairwise correlation coefficient according to Pearson.

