### **Conclusion:**

1. According to the NRI nutritional status assessment scales, the SGA mixed type of nutritional support at the time of transfer of patients to the specialized department and upon completion of this area of intensive therapy in the specialized department by 12-15 days of the postoperative period showed higher effectiveness in stabilizing the condition and maintaining the patients' caloric intake in a comparative aspect with the group of isolated enteral nutrition and parenteral nutrition.
2. Throughout the entire period of isolated enteral, parenteral and mixed nutritional support, all patients (100%) showed a relatively constant level of total blood protein.
3. In patients of all three groups, throughout the entire period of nutritional support, fluctuations in the level of basal metabolism were observed, which was due to the variability of body mass index and the dynamics of the temperature curve after surgery. In patients in the groups with enteral and parenteral nutrition, by the end of nutritional support (days 15-20), the level of basal metabolism was observed to approach its initial values. With a mixed type of nutrition, a statistically significant decrease in the level of basal metabolic rate was observed, which suggests a more effective coverage of the energy costs of patients with this option of replenishing nutritional ingredients.

**Researcher:** [name], PhD student KSMU

[contact].

e-mail: [contact].

[figure not shown]
Signature  17.03.2020

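### For normally distributed outcomes the three-group step is given as Student's t test, and no rule or adjustment governs the three pairs: about 12% false-positive risk per outcome and time point if read literally, 5% if gated.

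*Combined protocol and SAP*

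**What the plan says.** The report's *Methods of statistical data analysis* sets out three chains, each with a multi-group step followed by pairs.

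- **Normal data, separate arms:** Student's "t test for unrelated groups, first for 3 or more groups, and then in pairs for each pair using the" t test again.
- **Rank or non-normal data, separate arms:** "Kruskal-Wallis test or median test for 3 groups, and then pairwise or non-parametric Mann-Whitney test for each of the 3 pairs".
- **Repeated measures within patients:** a Kendall test, then Wilcoxon by pair of time points.

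The protocol's own section III.2, *Data analysis and monitoring*, is shorter. For judging differences it says only that Student's "t-test will be used. Also calculate the pairwise correlation coefficient according to Pearson".

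Neither section names an analysis of variance or F test, a significance level, a condition that pairs are tested only after a significant three-group result, or an adjustment for three pairs.

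The main comparative statement with a p-value concerns basal metabolism. In the mixed arm "there was a statistically significant decrease in the level of basal metabolism by 6.78"%, while in the two isolated arms "the level of basal metabolism was observed to approach its initial values". From this the report infers that "energy costs are more effectively covered with this option of nutritional support in a comparative aspect with isolated types nutrition", with a single p < 0.03. The *Conclusion* repeats the inference: "which suggests a more effective coverage of the energy costs of patients with this option of replenishing nutritional ingredients".

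**The concern.** Comparing three feeding methods is the purpose of the study, so the between-arm test carries the main message. A two-sample t test cannot test equality of three means, so in the normal-data branch nothing valid stands ahead of the three pairwise tests. The rank branch does have a valid first step (Kruskal-Wallis), but the text gives only an order of testing, not a condition. Taken literally, both branches allow three unadjusted looks at every outcome and time point.

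A reader therefore cannot tell whether the procedure holds about 5% or about 12% per outcome and time point. The printed results do not settle it. Several p-values are given one per arm. For total protein, for example, the mixed arm has its own p-value, and for the other two arms "differences in the dynamics of total protein levels were found at the level of a statistical trend", again with one p-value each.

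**Working it through.** The documents state no error rate, so there is no figure of theirs to reproduce first.

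**Inputs.** Arms of 31, 30 and 30 (report, *Research objectives*). Three pairs (*Methods of statistical data analysis*). Alpha and sidedness are not stated; two-sided 0.05 is assumed. The text points to 0.05: it uses 95% confidence intervals, calls p < 0.03 significant, and calls 0.108 and 0.129 a trend. Other assumptions: no true difference, normal data, equal SDs, one outcome at one time point.

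**Ungated pairs, analytic check.** The largest of three pairwise t statistics follows the studentized range:

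P(Q(3, 88) > √2 × t(0.975, 88)) = 12.13%.

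This uses a variance pooled over the three arms and treats them as equal in size, which is nearly true. Treating the pairs as independent would give 1 − 0.95³ = 14.3%, and the simple bound is 3 × 0.05 = 15%. Both overstate, because pairs share arms.

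**Simulation (400,000 null trials, 31/30/30).**

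| Procedure at alpha 0.05 | Chance of at least one false-positive pair |
|---|---|
| Three t tests, ungated | 12.1% to 12.2% (two runs) |
| Same, only if ANOVA F(2, 88) is significant | 5.0% |
| Bonferroni, 0.05/3 per pair | 4.4% |
| Mann-Whitney pairs, ungated (20,000 and 40,000 trials) | 11.5% to 11.7% |
| Same, only if Kruskal-Wallis is significant | 4.7% to 4.9% |

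**Other alpha values.** Ungated against F-gated: 2.7% and 1.0% at 0.01; 22.7% and 9.9% at 0.10.

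**Unequal SDs.** If the basal metabolism ± values (353.4, 330.5, 105.2) are read as SDs, a pooled F gate gives 5.7%, and a Welch F with Welch pairs 5.0%. Hence the Welch option in the fix.

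**Does a printed result depend on the gate?** *Results and discussion* prints 15 p-values in its text, and none names a pair of arms. The only case that can be recomputed is basal metabolism, and only if 2500.1 ± 353.4, 2350.0 ± 330.5 and 2250.0 ± 105.2 kcal/day are read as end values ± SD:

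- Three-group F test: F = 5.89, p = 0.0040 (Welch p = 0.0012).
- Mixed v enteral: pooled SD = √[(30 × 353.4² + 29 × 105.2²)/59] = 262.6; t = 250.1/(262.6 × √(1/31 + 1/30)) = 3.72; p = 0.0004.
- Mixed v parenteral: pooled SD = √[(330.5² + 105.2²)/2] = 245.2; t = 100/(245.2 × √(2/30)) = 1.58; p = 0.12.
- Enteral v parenteral: p = 0.092.

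The verdicts at 0.05 are the same ungated, gated or Holm-adjusted. On this reading the difference from the enteral arm is clear and that from the parenteral arm is not, with or without a gate.

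**Power cost.** If the mixed arm differs from both others by 0.75 SD, power for one pair is 82.1% ungated, 78.0% F-gated and 71.1% with Holm. At 0.5 SD it is 48.4%, 40.1% and 33.5%.

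**The case against.** **It is a slip for ANOVA.** The other two chains name real multi-group tests, and the text reads as a translation. This may well be right, and then only the name is wrong. The 12% belongs to the literal reading and is not an established property of what was run. Even so, naming ANOVA would leave the rule for the pairs and the alpha unstated. An order of testing is not a gate.

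**No printed result is shown to depend on it.** This stands. A reader might infer that the significant findings, or the preference for mixed nutrition, are products of unadjusted testing. The documents do not support that: no p-value is tied to a pair, and the one recomputable case has the same verdicts either way.

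**The p < 0.03 may be a within-arm test.** A reader might go further and infer that the between-arm difference would then fail. That cannot be shown. Such scenarios need an SD of change that is not printed. Change SDs of 300 or more, where the between-arm result turns borderline or worse, would need a baseline SD in the mixed arm of at least about 195 (300 − 105.2), against a printed 105.2. Reading ± as a standard error implies an SD of 353.4 × √31 ≈ 1,968 kcal/day in the enteral arm, which is implausible.

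**A better between-arm test would not rescue the energy-cost claim.** This also stands. Basal metabolism was calculated by Harris-Benedict from sex, age, weight and height, so over a few days only weight can move it within a patient. No test of that value can by itself show better coverage of energy costs.

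**The larger multiplicity remains.** The report lists about 20 measures, several repeated. If 20 were independent (an assumption), the chance of any false positive would be 1 − 0.8787²⁰ ≈ 92% ungated and 1 − 0.95²⁰ ≈ 64% gated. The fix controls error per outcome and time point only.

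**Conclusion.** The concern holds as a defect in the stated procedure. The normal-data branch names a two-mean test for three arms, and neither branch gates or adjusts the pairs. Read literally, this costs about 12% instead of 5% per outcome and time point, assuming two-sided alpha 0.05, no true difference, normality and equal SDs. If ANOVA with a gate was meant and run, the rate was already about 5% and the text should say so.

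It does not show that any printed p-value is wrong or that any conclusion is a false positive. It should be corrected because the between-arm comparison is the purpose of the study and the correction is cheap.

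**What to change.** 1. In *Methods of statistical data analysis*, replace Student's t test in the three-group step with one-way ANOVA (Welch version if variances are unequal), or with ANCOVA on the baseline value. If ANOVA was in fact run, say so. Keep Kruskal-Wallis for rank or non-normal data. Bring protocol section III.2 into line.
2. State alpha as 0.05, and one rule for the pairs in both branches: test them only after a significant three-group result (valid for exactly three arms), or use Holm or Tukey.
3. Re-run on the existing data. The study ended in March 2020 and the results are known, so describe this as a correction made afterwards, not as prespecified.
4. Label every p-value with its pair of arms, or as a within-arm change in a named arm.
5. In *Results and discussion* and the *Conclusion*, report between-arm tests of the basal metabolic rate for mixed v enteral and mixed v parenteral. Limit the statement to that calculated rate, or to a decrease within the mixed arm.

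The cost is a few sentences and a re-run in the same software. There is a small loss of power for a single pair, possibly fewer nominally significant results, and a softer statement on energy costs.
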